## **D. Subject Criteria**

### **D1. Inclusion criteria**

Patients of both genders and all races will be eligible for this study if they are between the ages of 20.0 and 75.0, have a BMI between 30.0 kg/m^2 and 45.0 kg/m^2, reside in a rural location as defined by Rural-Urban Commuting Area (RUCA) Codes, Urban Influence Codes, amount of agricultural income, and/or individual commuting patterns, and have clearance from their primary care provider to participate in a diet and exercise weight control intervention. Participants must have access to a telephone. One individual per household will be permitted to enroll in the study. Patients who are eligible but unable to attend at least some of the counseling visits according to the type, location, and frequency specific to each arm will be documented as eligible but declined, with the reason noted.

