### **Secondary aim 5: assess heterogeneity of treatment effects (HTE) across participants**

We anticipate treatment effects will vary across participants based on characteristics identified by the literature and by our patient partners as important for service utilization. Specifically, we hypothesize that DM and PCMH will show larger effects over FFS for racial/ethnic minorities (compared to White non-Hispanic), those with lower education (less than Bachelors degree), and those with lower income (e.g., less than \$50K household income). This is because the more intensive treatment in DM and PCMH may be especially important for subgroups who have fewer resources and face greater life stress, as is often the case for rural minorities in a predominantly White rural Midwestern region. We also hypothesize that DM and PCMH will show larger effects over FFS for participants who travel longer distances/have longer travel time to receive care or who are employed full-time because the traditional face-to-face office visit during regular clinic hours may limit their uptake of treatment. We will also explore interactions between treatment conditions and weight loss history (particularly any history of seeking assistance for weight loss) as participants with prior knowledge and skills for successful weight loss may benefit more from the brief counseling provided in FFS. Using separate hierarchical linear mixed models predicting weight loss over 24 months, we will examine interactions between each participant factor and treatment arms.

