### **Secondary aim 6: evaluate the reach and sustainability of the interventions with the RE-AIM framework (Reach, Adoption, Implementation, Maintenance)**

Adoption within KUMC-affiliated sites will be evaluated by comparing practice characteristics across participating and non-participating practices (that were contacted about the study) using two sample comparisons (chi square or t-tests). After aggregating to the practice level, patient-level factors for reach (e.g., participation rates) and implementation (e.g., session attendance, ratings of care) will be tested and compared across arms using separate analysis of variance (ANOVA) models. Maintenance of weight loss services at the practice-level will be reported as simple frequencies.

**Potential confounders:** For all statistical models, sensitivity analyses will be performed using the models above but also adjusting for potential confounders among the baseline variables identified as varying across arms based on their standardized differences.

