## **C2. Blinding**

Randomization happens at the practice level. Blinding practice staff or study staff is not feasible during a behavioral trial. However, throughout the study investigators and study personnel will communicate and

demonstrate equipoise (genuine uncertainty) with practice staff and patients about the relative benefit of the three arms.

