#### E5. Timeline (Figure 3)

The original funding period for this study was 5 years, January 1, 2015 to December 31, 2019. A global contract modification fully executed in February 2018 extended the period of performance through April 30, 2020. The final timeline is included in Figure 3. All project milestones, as required by PCORI, will be completed within this time frame. The study will be implemented in three cohorts, with 12 primary care practices in each cohort (4 in each of the 3 arms). Patient recruitment will begin in January 2016 for cohort 1, June 2016 for cohort 2 and September 2016 for cohort 3. Practices in the PCMH and DM arms will enroll 40 patients over a 6 month time period. The FFS arm will enroll 40 patients over a 9 month period (indicated in the timeline below with dotted lines). Each patient in all arms will be followed for 2 years. Analysis and dissemination of the primary outcomes will happen in the final 6 months of the project period.

Figure 3. Study Timeline

	Year 1 - 2015				Year 2 - 2016				Year 3 - 2017				Year 4 - 2018				Year 5 - 2019				Year 6 - 2020	
	Q1	Q2	Q3	Q4	Q1	Q2	Q3	Q4	Q1	Q2	Q3	Q4	Q1	Q2	Q3	Q4	Q1	Q2	Q3	Q4	Q1	Q2
Cohort 1	Study Preparation IRB Approval Practice Recruitment DSMB Charter Obesity Trainings			Practice Training	Recruitment		Phase 1		Phase 2										Analysis and Dissemination			
Cohort 2					Practice Training	Recruitment		Phase 1		Phase 2												
Cohort 3						Practice Training	Recruitment		Phase 1		Phase 2											

Figure 4. Study Flow

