#### **14. IRB-approved protocols**

All sites will use the same recruitment materials and IRB-approved protocol and consent form (consent form varying by arm). All practice staff who serve as research personnel will complete HSC training and training in protocols for collecting patient consent, conducting assessment visits, and conducting counseling visits (FFS and PCMH only). As a pragmatic trial, we will not strictly monitor adherence to counseling session guidelines but rather will offer training and support for the FFS and PCMH arms that is consistent with real-world models of care. As such, by design we are retaining the inherent differences in quality control and training in behavioral obesity treatment across the three arms, with the greatest level of training and quality control in the DM arm. In contrast, adherence to protocols for consenting patients and collecting data will be closely monitored. Initial training in study protocols will occur in-person during a central training at the start (see I5 below). Consenting protocols and assessment protocols will be demonstrated and practiced. Ongoing training will occur in-person during routine visits made by the Practice Coordinator, as well as through use webinars, and a written Standard Operating Procedures manual provided to each practice. The Practice Liaison at each practice will be trained to help ensure that only HSC-approved study materials are used and that the HSC protocol is followed. Practice Coordinators will oversee adherence to the protocols at the clinics by working closely with the Practice Liaisons. The Practice Coordinator will meet regularly with the Practice Liaison by phone and email and will visit the practice in-person at a minimum twice per year with more visits as needed.

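### Enrolment depends on being able to attend the practice's own visit format after its arm is fixed, and the primary model names no baseline covariates to offset any resulting imbalance

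*Combined protocol and SAP*

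**What the plan says.** **Allocation and order.** Section II.C2 states that "Randomization happens at the practice level" and that "Blinding practice staff or study staff is not feasible during a behavioral trial". No single sentence says that patients enter after allocation, but several places imply it. The consent form differs by arm (II.I, IRB-approved protocols). The enrolment window also depends on the arm: "Practices in the PCMH and DM arms will enroll 40 patients over a 6 month time period" (II.E5), while FFS practices have 9 months.

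**Attendance clause.** The eligibility criteria in II.D1 and II.D2 are common to all arms. II.D1 then makes a provision for otherwise eligible patients who are "unable to attend at least some of the counseling visits according to the type, location, and frequency specific to each arm". They are not called ineligible; the same section says that each case "will be documented as eligible but declined, with the reason noted".

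**Formats.** FFS offers 15-minute individual clinic visits, likely in working hours. PCMH offers 60-minute clinic groups, possibly in the evening, with a phone option later. DM offers 60-minute phone groups in set slots (II.E2a Table 1, II.E2c, II.F4).

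**The protocol's own expectation.** For patients who travel further or work full-time, the Aim 5 text in II.C1 says that "the traditional face-to-face office visit during regular clinic hours may limit their uptake of treatment". The fee-for-service part of I.B3 makes the same argument.

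**Analysis.** The primary hierarchical linear mixed model accounts for clustering by clinic and repeated measures (II.C1, Primary aims 1-3). It names no baseline covariates. Adjustment appears only under Potential confounders, as sensitivity analyses that repeat the models while "adjusting for potential confounders among the baseline variables identified as varying across arms based on their standardized differences".

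**The concern.** In a cluster trial, randomisation balances practices. The patients analysed are balanced in expectation only if entry to the sample does not depend on the arm. Here the same patient might enrol at a DM practice and be logged as declining at an FFS practice, purely because of the visit format. The protocol names two characteristics, distance and full-time work, on which this could happen.

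Two things are at stake. First, if those characteristics, or others linked to them, predict 24-month weight change, the PCMH–FFS and DM–FFS contrasts combine the effect of the care model with a difference in patient mix. Second, Aim 5 asks whether the advantage over FFS is larger in distant and full-time-employed patients. If the FFS patients in those groups are the ones who could manage the visits anyway, the interaction could look smaller than it is.

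Intention-to-treat analysis and maximum likelihood for missing weights do not help, because the patients concerned never enter the data set.

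**Working it through.** **1. Does the mechanism follow from the text?** Set side by side, the passages say that the arm is fixed at practice level, the arm is known at consent, ability to attend is judged against that arm's format, and the protocol expects format to affect access for identifiable patients. Together these give a route to differential selection. They do not show how many patients take it.

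**2. The plan's own precision (II.C3).** Inputs: 12 practices per arm, 40 patients each, ICC 0.05, SD 8 kg, effect 2.75 kg, type I error 0.025 per comparison. Sidedness is not stated; two-sided is assumed.

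- Design effect: 1 + (40 − 1) × 0.05 = 2.95
- Effective n per arm: 480 / 2.95 = 162.7
- SE of a contrast: 8 × √(2 / 162.7) = 0.887 kg
- Power (normal approximation): Φ(2.75 / 0.887 − 2.241) = 0.805

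This reproduces the stated 80%, so the sample-size figure is not in question here.

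**3. Scale of a possible bias.** Let Δp be the between-arm difference in the enrolled share of some patient type, and g the difference in 24-month weight change between that type and the rest under the same treatment. Then bias b = Δp × g. **The documents give neither quantity. Both ranges below are assumptions.**

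- Type I error with bias b: 1 − Φ(2.241 − b/SE) + Φ(−2.241 − b/SE)
- Power if the bias runs against the active arm: Φ((2.75 − b)/SE − 2.241)

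| Δp | g (kg) | b (kg) | b as % of 2.75 kg | Type I error (nominal 0.025) | Power if b opposes active arm |
|---|---|---|---|---|---|
| 0.05 | 1 | 0.05 | 1.8 | 0.025 | 0.789 |
| 0.10 | 1 | 0.10 | 3.6 | 0.026 | 0.772 |
| 0.20 | 2 | 0.40 | 14.5 | 0.040 | 0.658 |
| 0.30 | 2 | 0.60 | 21.8 | 0.061 | 0.572 |
| 0.30 | 3 | 0.90 | 32.7 | 0.111 | 0.438 |

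The lower rows need both a large difference in mix and a strong prognostic factor. A bias of 0.60 kg is below one standard error (0.887 kg); 0.90 kg is about one. Unlike sampling error, a bias does not shrink as the sample grows.

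**4. What the safeguards cover.** Decline reasons (II.D1) and reach comparisons (II.C1 Aim 6; II.E2f Table 6) describe selection but do not enter the weight analysis. The sensitivity analysis does enter it, but only for measured variables picked after imbalance is seen, with no threshold given for the standardised difference. The Aim 5 models include distance or travel time and employment, but as separate interaction models and not as adjustment of the primary contrast.

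**The case against.** The strongest reply is that the clause is not an exclusion at all. Eligibility is the same in every arm, the threshold is only some visits, and a patient who could attend none would probably decline without the sentence. On that view the clause merely records what happens in any cluster trial that recruits after allocation. This stands as a description. It narrows the point to a selection risk that the trial shares with others of its kind and for which the primary analysis makes no provision.

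A reader might infer that full-time workers and distant patients are removed from FFS while DM loses few. The documents do not say so. They say only that FFS visits may limit uptake. FFS visits are short and practices may choose their own scheduling (II.E2c), PCMH groups may meet in the evening (II.F4), and DM calls run at set times. Distant and employed patients who can attend some visits remain in every arm. Section III.C4 expects attendance to differ by arm and uses retention contacts to secure the assessment visits, so low attenders should stay in the analysis. Aim 5 could be attenuated, but its subgroup is not eliminated.

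It is also fair that the plan holds more than one safeguard, and that common recruitment materials and central phone screening (III.B) limit arm-specific recruitment.

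On direction, if FFS loses patients who would have done badly there, FFS is flattered and the superiority tests become conservative. That is plausible on the protocol's own reasoning, but it is not established. Those patients' prognosis is unknown, and PCMH and DM have constraints of their own.

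Finally, the trial is pragmatic, and acceptability of a format is part of what it studies. But the plan places reach under Aim 6 and weight under Aims 1 to 3. Measuring the first does not separate it from the second.

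**Conclusion.** The point holds as a risk of differential selection, of unknown size and direction, that the primary analysis does not address. It rests on two readings: that patients are enrolled once their practice's arm is known, which is inferred from the arm-specific consent form and enrolment windows, and that ability to attend a format is related to 24-month weight change, which the documents leave open.

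The range of 0.05 to 0.90 kg illustrates scale under assumed inputs. It is not an estimate, and the lenient attendance threshold makes the low end quite possible. A reader might conclude that randomisation has failed to make the arms comparable; the documents do not support that. They show a route by which comparability could be lost, with no evidence that it has been. This is a cheap improvement to the plan, not a flaw that invalidates the primary contrasts.

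**What to change.** 1. **Primary model.** By dated amendment, before outcomes are examined by arm, prespecify travel distance or time, employment status and baseline weight as fixed covariates in the primary mixed model. Age and sex are optional. Do not rely on the sensitivity adjustment chosen from observed imbalance; it can remain as a supplement.
2. **Reporting.** Show eligible-but-declined counts and reasons by arm next to the primary result, so that readers can judge how much selection took place.
3. **If recruitment is still open (optional).** At the central phone screen, ask each candidate about ability to attend each of the three formats, before the arm is discussed where possible. Then repeat the primary contrasts in those able to attend any format. Because staff are not blinded and providers may refer patients directly, asking before the arm is known cannot be guaranteed.

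**Cost.** Items 1 and 2 need no new data collection. Weight, employment status, physical address and date of birth are taken at baseline (II.E2e), Aim 5 already needs distance or travel time, and decline reasons are already recorded. The cost is a little analysis work, with a possible gain in precision. Item 3 adds a few screening questions. Adjustment reduces bias from measured factors only; selection on unmeasured ones remains and should be stated as a limitation.

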### **D2. Exclusion criteria**

As a pragmatic trial, the exclusion criteria were kept minimal to maximize generalizability and reduce patient screening burden but include necessary exclusions to minimize safety concerns and major confounds on the primary endpoint. Individuals with a history of bariatric surgery or planned bariatric surgery within 2 years, myocardial infarction (MI) in the last 6 months, stroke in the last six months, new cancer diagnosis in the last six months (with the exception of non-melanoma skin cancer), pregnancy in the last 6 months/planned within the next 2 years or currently lactating, and serious medical conditions where weight loss is contraindicated will be excluded from the study. A history of miscarriage in the last 6 months, in and of itself, will not be considered an exclusion. Individuals with end stage renal disease, known GFR < 25, current or anticipated dialysis or transplant within the next two years will be excluded; a history of renal transplant is not an exclusion per se if patient does not meet stated renal criteria. Similarly, patients with end stage liver disease or anticipated liver transplant within the next two years will be excluded; a history of liver transplant is not an exclusion per se, if patient does not meet stated hepatic criteria. Other medical contraindications will be determined by the patient's PCP, and documented PCP clearance will be obtained. Participants who are already enrolled in, or planning to enroll in another research study where weight loss is targeted will be excluded. Participants who plan to relocate outside of their provider's service area or who

plan to leave their primary care clinic in the next two years will be excluded. Participant eligibility screening, assessments, and counseling sessions will be delivered in English; individuals who do not speak English will be unable to participate in the study.

### **D3. Withdrawal/termination criteria**

#### *Medical Removal for Safety Purposes*

Participants who experience an injury or new medical condition for which exercise or weight loss may be contraindicated will be asked to see their medical provider for treatment and evaluation. After consultation with the KUMC study physician and/or the practice study PCP, participants will be removed from the study if the onset of a medical condition contraindicates their participation. Participants will be removed for pregnancy past the first trimester and bariatric surgery while on study.

Members of the study team, the care coordinators/counselors, and the PCPs retain the right to remove a participant from the study if it is deemed that the participant is unsuitable for group or individual weight loss counseling sessions due to behavioral problems caused by mental illnesses, substance abuse, or any other reason.

### **D4. Other studies**

Participants enrolled in this study may not participate in other research studies where weight loss is targeted.

## **E. Specific Methods and Techniques Used Throughout the Study (Figure 4. Study Flow; page 26)**

### **E1. Laboratory tests**

Blood draws will occur at baseline, 6 months, and 24 months. Blood draws will be collected at the local practices by a phlebotomist or nurse. The practice staff will monitor and record self-reported fasting compliance. The collection, processing, analysis and storage of samples will differ depending on the site.

#### *KUMC and UNMC Affiliated Practices*

A phlebotomist or nurse will collect 5 ml of blood in an appropriate vacutainer-type tube specified by the analyzing laboratory. Practices with in-house analyzing labs will process the samples onsite prior to analysis according to their standard operating procedures. Practices that send samples off-site for testing will send either whole blood samples off-site or will process samples prior to shipment, again, according to their standard operating procedures. Study samples will be analyzed for fasting glucose and a lipid panel, to include LDL, HDL, triglycerides, and total cholesterol. Laboratory results will be sent to the patient's PCP per their normal standard operating procedures. Practice staff, in turn, will provide the laboratory results to KUMC study personnel.

#### *Marshfield Clinic Health Practices*

The ten Marshfield Clinic Health Practices participating in the study will use Marshfield Laboratories as their clinical laboratory testing facility. Marshfield Clinic Research Institute's (MCRI) Integrated Research and Development Laboratory (IRDL) will be used as the bio-storage facility for the study. All freezers, refrigerators, centrifuges, and analytical instruments used for the study are monitored at least annually for safety and performance; daily temperature monitoring of refrigerators and freezers is conducted.

Practices will be provided study lab kits for efficient specimen collection and processing. Kits will be assembled by study staff members or IRDL staff, and will include the following: a biohazard bag, absorbent material, specimen collection containers to include one lithium-heparin green top plasma tubes (GTPT) (5

ml) and two lavender top tubes (LTT), a sample transfer tube, a clinical lab requisition (for Marshfield Lab use) and a processing lab slip (for IRDL use). Staff will use the kits to obtain samples from the subjects at their scheduled data collection visits. A total of 15 mls of blood will be collected from each patient at each visit when labs are required.

Staff at practices remote to the main Marshfield Lab will process the GTPT samples on site in accordance with laboratory protocols. The processed GTPT samples and LTT tubes will then be sent to Marshfield Lab via the Marshfield Lab courier system. The courier service provides regular daily stops at the practices (M-F). Samples collected at practices located on the Marshfield Main campus will not be processed at the practices, but rather transported to the main lab for processing and analysis via the laboratory's automated transport system.

All samples will be received by the Marshfield Labs specimen processing staff. The GTPT aliquoted plasma will be used to assay the fasting glucose and lipid panel (total cholesterol, triglycerides, HDL, LDL). Test results will be imported into each patient's MCHS electronic health record. Study staff will enter the laboratory data into REDCap, the study database. Primary care providers will be automatically notified per normal procedures when results are flagged for review.

LTT samples and the IRDL lab slip will be retrieved from the Marshfield Lab by IRDL staff. Samples will be processed in accordance with instructions on the lab slip. The resulting plasma and buffy coat layer will be stored separately in multiple aliquots. Each processed sample will retain Study ID and visit number identification and will be stored in a -80°C freezer. Samples from patients who do not give consent for future storage and use will be destroyed at specific time points during the study period.

